4.4.2.1 Biomarker Outcome Measures

- Change in t-tau levels in CSF from baseline at Week 104
- Change in p-tau levels in CSF from baseline at Week 104
- Change in $A\beta_{1-42}$ levels in CSF from baseline at Week 104
- Change in $A\beta_{1-40}$ levels in CSF from baseline at Week 104
- Change in $A\beta_{1-42} / A\beta_{1-40}$ ratio in CSF from baseline at Week 104
- Change in pTau / tTau ratio in CSF from baseline at Week 104
- Change in pTau / $A\beta_{1-42}$ ratio in CSF from baseline at Week 104
- Change in $A\beta_{1-42}$ levels as measured by PET scan from baseline at Week 104
- The change from baseline in hippocampal volume at Week 104
- The change from baseline in whole brain volume at Week 104
- The change from baseline in ventricular volume at Week 104

4.5 SAFETY ANALYSES

Descriptive statistics will be used to analyze all safety data. The outputs defined in this section will be produced using the safety analysis population, unless otherwise specified.

For all safety analyses, Day 1 will be defined as the start date of double-blind randomized treatment.

4.5.1 Exposure of Study Medication

Exposure to study drug will be summarized using the following descriptive statistics:

- Duration of treatment (defined as the time from the date of first treatment to date of last treatment in Part 1 of the study)
- Duration of treatment at the 105mg dose for patients whose highest dose was 105mg
- Duration of treatment at the 105mg dose for patients who reached the 225mg dose
- Duration of treatment at the 225mg dose for patients who reached the 225mg dose
- Cumulative dose
- Total patient years on gantenerumab: Time from first dose in double-blind until 28 days after last dose in double-blind or first dose in OLE (whichever occurs first).

- Total patient years on 105mg gantenerumab
- Total patient years on 225mg gantenerumab

4.5.2 Adverse Events

Adverse events will be coded using the Medical Dictionary for Regulatory Activities (MedDRA) version that is current at the time of the analysis (Version 20). For each treatment group, the frequency of each adverse event preferred term will be defined as the number of patients experiencing at least one occurrence of the event. As patients will have had different amounts of time in the study, the incidence rate will be calculated as the frequency count divided by the total number of patient years exposure for the patients in the population and treatment group specified. Each table will also present the overall number of patients experiencing at least one adverse event and the total number of adverse events reported. Patient listings will contain preferred terms and comments for each event. In summary tables, adverse events will be sorted by body system (in decreasing order of overall incidence), then by preferred term (in decreasing order of overall incidence).

The following safety information will be summarized:

- Adverse events
- Serious adverse events
- Study drug–related adverse events
- Study drug–related serious adverse events
- Adverse events leading to discontinuation of study treatment
- Adverse events leading to dose reduction
- Adverse events leading to no up-titration from 105mg to 225mg at Week 28
- Adverse events leading to dose held

The following data handling rules will be applied for all adverse event summary tables:

- Multiple occurrences of the same adverse event in 1 patient will be counted only once.
- Missing preferred terms (PTs) will be presented as the investigator’s term, preceded by “NO_PT_Found” in all outputs. Missing super-class terms (SCTs) will be

presented as “<NO_SCT_FOUND>” in all outputs. All cases of missing PTs should be resolved at the time of the final database closure.

- Events that are missing both onset and end dates will be considered to have started after the first dose of study treatment and the duration will be set to missing.
- If the onset date is missing, and the end date is on or after the first dosing date or unresolved or missing, then the event will be to have started after the first dose of study treatment.

The following data handling rules will also be applied for specific tables:

- An adverse event will be included in the summary table of adverse events leading to study drug discontinuation if the “action taken with blinded gantenerumab” drop-down menu on the Adverse Event CRF is checked “drug withdrawn”.
- In the summary table of adverse events by intensity, if a patient has more than one occurrence of an event, the event with the most severe intensity will be counted. If the intensity of an adverse event is missing, then the adverse event will be included only in the total number of events column, and not in the count of patients with the event by intensity.

For scientific interpretation it is important to separate ARIA-H and ARIA-E events in listing and tables. However, using MedDRA standards, both get mapped to the preferred term 'AMYLOID RELATED IMAGING ABNORMALITIES'. Furthermore, there are some additional terms that the Clinical Science and Safety Science teams deem to be ARIA-E or ARIA-H that have separate MedDRA preferred terms. To overcome this, baskets will be implemented to summarize all ARIA-H events together and all ARIA-E events together. These baskets are defined below:

- ARIA-E
 - Preferred term: 'VASOGENIC CEREBRAL OEDEMA' or
 - Lower level terms: 'AMYLOID RELATED IMAGING ABNORMALITY-OEDEMA/EFFUSION' or 'AMYLOID RELATED IMAGING ABNORMALITY-OEDEMA/EFFUSION' or 'ARIA-E'
- ARIA-H

- Preferred term: 'CEREBELLAR MICROHAEMORRHAGE' or 'CEREBRAL HAEMOSIDERIN DEPOSITION' or 'CEREBRAL MICROHAEMORRHAGE'
- Lower level terms: 'AMYLOID RELATED IMAGING ABNORMALITY-MICROHAEMORRHAGE AND HAEMOSIDERIN DEPOSITS' or 'AMYLOID RELATED IMAGING ABNORMALITY-MICROHEMORRHAGES AND HEMOSIDERIN DEPOSITS' or 'ARIA-H'

Instances where an AE has MedDRA preferred term 'AMYLOID RELATED IMAGING ABNORMALITIES' but does not fit into one of the two baskets above, will be assessed on a case-by-case basis.

In the summary table of adverse events by relationship to study drug, if a patient has more than one occurrence of an event, the most closely related event will be counted. If the relationship of an adverse event is missing, then the adverse event will be included only in the total number of events column, and not in the count of patients with the event by relationship.

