5.1.4 Management of Selected Adverse Events

5.1.4.1 Dosing Strategy and ARIA-Related Dose Adjustments in Part 1

All patients randomized to gantenerumab will receive a dose of 105 mg q4w for the first 24 weeks and, if eligible, the dose will be up-titrated to 225 mg q4w for the remainder of the study regardless of APOE ϵ 4 status. Patients will undergo brain MRI examinations for ARIA-related safety monitoring as specified in the schedule of assessments. MRI after the Week 24 dose will determine eligibility for dose titration starting with the Week 28 dose. Patients will be eligible to receive 225 mg q4w starting with Week 28 if no ARIA-E and no more than one new microbleed are detected on any MRI scan up to and including the post-Week 24 MRI. In addition, the following dose adjustment and discontinuation rules for MRI safety-related findings will apply:

- At any time during the study upon emergence of single ARIA-E >2 cm or multiple ARIA-E, study drug will be withheld until the ARIA-E has resolved or significantly decreased and stabilized. Dosing can then be restarted with 105 mg q4w. If ARIA-E recurs (e.g., initial lesion increases in size, new lesion is detected in a different location), the patient will be discontinued from treatment (irrespective of the size of ARIA-E).
- A single ARIA-E finding of ≤ 2 cm does not require any dose change. Upon detection of such an ARIA-E finding, monthly MRI monitoring will be performed until the event has resolved.
- For patients on the 225 mg dose of gantenerumab who develop two new microbleeds on a single scan or three or four new microbleeds cumulatively the dose will be reduced to 105 mg. All patients who develop five or more new microbleeds cumulatively will be discontinued from study treatment.
- In case of both ARIA-E and ARIA-H, the most conservative approach should be followed.
- In case of ARIA findings, a PK sample will be obtained as soon as is practical once the site becomes aware of the occurrence or worsening of ARIA-E or ARIA-H (e.g., unscheduled visit).

The iDMC will continue reviewing the incidence of ARIA and may recommend adjustment of the dosing regimen for the overall study population or in a specific APOE ϵ 4 genotype.

5.1.4.2 Dosing Strategy and ARIA-Related Dose Adjustments in Part 2

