5.3.5.1 Injection Reaction

Individual signs and symptoms of injection-site reactions (e.g., erythema, pain) should be reported on the Injection-Site Reaction eCRF. The overall diagnosis of injection-site reaction should be captured on the Adverse Event eCRF. Systemic reactions should be recorded as a single diagnosis.

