5.3.5.4 Persistent or Recurrent Adverse Events

A persistent adverse event is one that extends continuously, without resolution, between patient evaluation timepoints. Such events should only be recorded once on the Adverse Event eCRF, unless the severity increases. If a persistent adverse event becomes more severe, it should be recorded as a separate event on the Adverse Event

eCRF. The initial (less severe) adverse event report should be updated to indicate that the event resolved on the date just prior to the day the event became more severe. If a persistent adverse event becomes serious, it should be recorded as a separate event on the Adverse Event eCRF and reported to the Sponsor immediately (i.e., no more than 24 hours after learning that the event became serious; see Section 5.4.2 for reporting instructions). The initial (non-serious) adverse event report should be updated to indicate that the event resolved on the date just prior to the day the event became serious.

A recurrent adverse event is one that resolves between patient evaluation timepoints and subsequently recurs. Each recurrence of an adverse event should be recorded separately on the Adverse Event eCRF.

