4.5.3 MRI Safety Findings and Injection-Site Reactions

The incidence of ARIA-E, ARIA-H and other MRI findings as well as injection-site reactions will be listed and summarized by treatment group. In addition, the MRI data will be summarized by *APOE* genotype and by time-window.

Sites were asked to also capture both ARIAs leading to dose modification and injection site reactions as AEs.

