AESIs are discussed in more detail in the study protocol Section 5.2.3. AESIs in this study will be captured by recording all case details on the AE eCRF.

In the tables of study drug related AEs or SAEs, if a patient has more than one occurrence of an event, the most closely related event will be counted. If the relationship of an AE to the study drug is missing, then the AE will be included only in the total number of events column, but not in the count of patients with the related event.

The AE and SAEs incidence rates per patient-years in the OLE will be calculated as the total number of occurrences divided by the total duration of treatment in the OLE in patient-years for each specified population or group. The duration of treatment in the OLE is from the start of OLE until 4 weeks after last dose in the OLE.

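### The Part 1 AE incidence rate counts each patient once but does not stop exposure at the first event, so for common terms it falls modestly below the first-event rate if event and exposure windows match

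*SAP*

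**What the plan says.** Part 1 SAP 4.5.2 takes the frequency of a preferred term to be "the number of patients experiencing at least one occurrence of the event", and its data-handling rules count repeats in one patient once. Because patients differ in time on study, it then forms an incidence rate, the "frequency count divided by the total number of patient years exposure for the patients in the population and treatment group specified".

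Part 1 SAP 4.5.1 gives the patient-years rule for gantenerumab. Time runs from first double-blind dose to the earlier of 28 days after the last double-blind dose and the first OLE dose. Neither section ends a patient's time at the first event, and the placebo rule is not written out. 4.5.2 does not say that the numerator is limited to onsets within this window. Protocol 5.3.1 has Part 1 AEs reported for 52 weeks after the last dose.

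Other parts of the plan bear on the point:

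- Part 1 SAP 4.5.2 adds: "Each table will also present the overall number of patients experiencing at least one adverse event and the total number of adverse events reported". Section 4.5 makes all safety analysis descriptive, and 4.5.3 separately summarises MRI findings and injection-site reactions by treatment group.
- On what reaches the AE form, Protocol 5.3.5.1 says: "The overall diagnosis of injection-site reaction should be captured on the Adverse Event eCRF". Part 1 SAP 4.5.3 says: "Sites were asked to also capture both ARIAs leading to dose modification and injection site reactions as AEs".
- In OLE SAP 5.7.2, the AE and SAE incidence rates "will be calculated as the total number of occurrences divided by the total duration of treatment in the OLE in patient-years".

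**The concern.** After a patient's first event of a term, that patient can add nothing more to the numerator but goes on adding to the denominator. The quotient is therefore neither a first-event rate per time at risk nor a rate of events. The gap between it and the first-event rate widens as the term becomes more common or occurs earlier.

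This rate is the only exposure-adjusted AE measure in 4.5.2, and it was adopted because time on study is unequal. A reader is likely to take it as the rate at which patients first have the event and to compare the arms on it. Injection-site reactions are the clearest case, because they are an identified risk, they are common on active treatment and they are recorded as AEs. ARIA is a weaker example, because sites were asked to enter as AEs only those ARIAs that led to dose modification.

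**Working it through.** **Inputs.** The plan states no AE rate, so there is no figure to reproduce. The proportions come from Study WN25203 (Protocol 1.3.3). Injection-site reactions occurred in 4.5% on placebo, 18.8% on 105 mg and 23.1% on 225 mg; ARIA-E occurred in 12.3% on 225 mg. Both injection-site figures for active treatment are used because Part 1 gave the two doses in sequence (Protocol 5.1.4.1: "All patients randomized to gantenerumab will receive a dose of 105 mg q4w for the first 24 weeks", then 225 mg if eligible). Common follow-up T, constant hazard and a numerator limited to the exposure window are assumptions.

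**Shortfall.** The stated rate is p/T. The first-event rate under constant hazard is −ln(1−p)/T. Their ratio is p/[−ln(1−p)], and T cancels.

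| p | −ln(1−p) | Ratio | Shortfall |
|---|---|---|---|
| 2.0% | 0.0202 | 0.990 | 1.0% |
| 4.5% | 0.0460 | 0.977 | 2.3% |
| 12.3% | 0.1312 | 0.937 | 6.3% |
| 18.8% | 0.2083 | 0.903 | 9.7% |
| 23.1% | 0.2627 | 0.879 | 12.1% |

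The shortfall reaches 5% at p = 9.8% and 10% at p = 19.3%. With T = 2 years and p = 23.1%, the rates are 11.6 and 13.1 per 100 patient-years.

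**Unequal follow-up.** In a simulation of 400,000 patients with follow-up uniform on 0.25 to 2 years (assumption), a term affecting 13.4% had a ratio of 0.917. The common follow-up formula gives 0.134/0.1439 = 0.931. The size is similar.

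**Onset timing.** If first events fall on average at a fraction u of exposure, the shortfall is p(1−u). For p = 23.1%, u = 0.10, 0.25 and 0.50 give 20.8%, 17.3% and 11.6%.

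**Between arms, similar timing.** Against 4.5% on placebo:

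- 18.8%: ratio 0.188/0.045 = 4.18, against 0.2083/0.0460 = 4.52. Difference 0.143/T against 0.1622/T, 12% too small.
- 23.1%: ratio 0.231/0.045 = 5.13, against 0.2627/0.0460 = 5.70. Difference 0.186/T against 0.2166/T, 14% too small.

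**Between arms, different timing.** With onset at 90% of exposure on active and 10% on placebo, the first-event ratio is [0.231/(0.769 + 0.231×0.9)] / [0.045/(0.955 + 0.045×0.1)] = 5.04. The stated ratio of 5.13 is then slightly too large.

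**Numerator window.** At 23.1%, the stated rate equals the first-event rate once the counted proportion rises to 26.3%. First events in the later follow-up from about 3.2% more patients (0.2627 − 0.231) would therefore remove the shortfall.

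**Sampling error.** Splitting the 389 Part 1 patients 1:1 (assumption) gives 194.5 per arm, or about 44.9 against 8.75 patients with an event. SE(log ratio) = √(1/44.9 + 1/8.75) = 0.37, and 5.13 × exp(±1.96 × 0.37) gives about 2.5 to 10.6. The value 5.70 lies well inside.

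**Part 1 against OLE definition.** With 23.1% affected and T = 2 years, the Part 1 rule gives 11.6 per 100 patient-years whatever the recurrence. The OLE rule gives 11.6, 23.1 or 57.8 with 1, 2 or 5 events per affected patient (assumptions).

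**The case against.** The strongest reply is that patients over total exposure is a recognised crude exposure-adjusted summary, openly defined, and 4.5.2 never claims that it estimates a first-event hazard. That stands: the arithmetic is not wrong, and a shortfall exists only relative to the quantity that a reader would probably have in mind. It is also true that the SAP plans no rate ratio, rate difference or test on AEs, that patient counts and total AEs appear beside the rate, and that the illustrative proportions come from another trial in prodromal disease with separate dose arms.

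A reader might infer that the Part 1 rates are certainly too low and that the comparison of arms is certainly biased toward no difference. The documents do not support that. The SAP does not restrict the numerator to the exposure window, AE reporting continues to 52 weeks after the last dose, and the timing example above reverses the between-arm effect.

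A reader might also infer that the two SAPs make Part 1 and OLE safety results wrongly comparable. They serve separate reports, and neither plans to compare AE rates between the parts. The shared name is a labelling weakness.

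Nor is switching Part 1 to the OLE rate a free remedy. Protocol 5.3.5.4 says "Each recurrence of an adverse event should be recorded separately on the Adverse Event eCRF", but it also has a persistent AE entered again when it becomes more severe or serious. Raw counts would then take one continuous episode as two.

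**Conclusion.** The point holds as a minor one. The Part 1 rate mixes a once-per-patient count with exposure that continues after the event. If the numerator is limited to onsets in the exposure window, it lies below the first-event rate. The shortfall is negligible for rare terms and about 10% to 12% for a term as common as injection-site reactions were in WN25203, under constant hazard and common follow-up; earlier onset makes it larger. Attenuation of a ratio between arms is the usual direction when exposure and timing are similar, but it is not assured. The size is well inside sampling error for a trial of 389 patients, and the tables are descriptive. The change is still worth making because a better definition costs little, and the present text leaves both the numerator window and the placebo denominator unstated.

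**What to change.** In Part 1 SAP 4.5.2, define the rate as patients with a first event of the term divided by time at risk. Time at risk runs from first double-blind dose to the earliest of the first event of that term, 28 days after the last double-blind dose, and first OLE dose. Apply the same rule in both arms and count only events with onset in that window.

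Add an onset-date imputation rule. The current rules place events with missing onset after first dose but give them no date, so time at risk would be undefined. The rule should cover partial dates too.

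If an occurrence rate is also reported, give it its own name, and first merge the records of one persistent AE that was re-entered because it became more severe or serious.

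The cost is SAP wording, one derived time-at-risk variable per term and a date-imputation rule. No new data are needed.

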4.5.3 MRI Safety Findings and Injection-Site Reactions

The incidence of ARIA-E, ARIA-H and other MRI findings as well as injection-site reactions will be listed and summarized by treatment group. In addition, the MRI data will be summarized by *APOE* genotype and by time-window.

Sites were asked to also capture both ARIAs leading to dose modification and injection site reactions as AEs.

4.5.4 Laboratory Data

Laboratory data will be summarized for each assessment using descriptive statistics of absolute values, change from baseline values and percent change from baseline. The proportion of patients who develop marked abnormalities during study treatment, on the basis of the National Cancer Institute Common Terminology Criteria for Adverse Events (NCI CTCAE v4.0) and the International Standard for Handling and Reporting of Laboratory Data (COG 2.2) will be summarized.

4.5.5 **Vital Signs**

Vital signs assessments include systolic blood pressure, diastolic blood pressure, and pulse measured throughout the study. Summaries of vital sign measurements at each assessment time-window using descriptive statistics will be generated for the actual values, the change from baseline and the percent change from baseline.

4.5.6 **Electrocardiograms**

Descriptive statistics will be generated for the actual values, the change from baseline and the percent change from baseline for the following parameters:

- Heart rate
- PQ (PR) interval
- QRS interval
- QT interval
- RR interval
- QTcB and QTcF

Duration of the QT interval is inversely correlated with the corresponding heart rate, so it should be corrected relative to heart rate to allow a reliable interpretation of changes in the QTc interval independent of the changes in the heart rate. The QT intervals will be corrected for the heart rate using Bazett's and Fridericia's formulae (QTcB and QTcF, respectively) as follows:

- The QTcB value will be calculated as the QT interval (in milliseconds) divided by the squared root of the RR interval (in seconds).
- The QTcF value will be calculated as the QT interval (in milliseconds) divided by the cube root of the RR interval (in seconds).

In some cases, multiple ECGs were performed in error. In these cases, the mean values across the ECGs should be used.

4.5.7 **Deaths**

Deaths will be listed.

4.5.8 Sub-group analysis

All safety and efficacy analysis will also be performed in the sub-group of patients who were enrolled in Japan and by APOE e4 carrier/non-carrier status.

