6.1.6 Exploratory Analyses

An analysis will be performed to explore association of the treatment effect with patient genotypes to assess the influence of the APOE $\epsilon 4$ status and $Fc\gamma$ receptor genotypes on the gantenerumab treatment effect, the primary efficacy variable, and selected safety parameters and summarized by each of the genotypes. Inferential statistics may be applied in case the difference is clinically relevant.

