6.1.7 Subgroup Analyses

Since this is a global study, the effect of some demographic variables and baseline characteristic such as race and region on efficacy and safety will be summarized within subgroups using descriptive statistics (please see subgroups below). Additional exploratory analyses of efficacy results may be performed using an MMRM model, with the subgroup, a treatment-by-subgroup interaction term, and a subgroup-by-time interaction terms included along the independent effects described above. This

exploratory subgroup analysis may be important in understanding the effect of these variables on efficacy and safety. Such exploratory analyses will be performed primarily in the case where the descriptive statistics results indicate substantial differences between the subgroups.

The following variables will be used to define the subgroups for these analyses:

- Sex
- Age
- Race
- APOE ϵ 4 status
- Fc γ receptor genotype
- Region

Additional subgroup analyses may be performed with subgroups defined based on baseline levels of CSF t-tau, p-tau, t-tau to A β 1–42 ratio, and p-tau to A β 1–42 ratio.

Since Part 1 (i.e., the double-blind period) has been suspended and replaced by an OLE, the primary and key secondary efficacy analyses will not be performed. However, exploratory and descriptive analyses will be conducted at the end of Part 1.

6.2 ANALYSES IN PART 2

As Part 2 is an OLE, regular safety analyses will be conducted as described in Section 6.1.4. In addition, descriptive statistics and changes from baseline will be used to explore clinical findings (including efficacy, global functioning, and biomarkers). PK analysis will be conducted according to Section 6.1.5.

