1. BACKGROUND

This document describes the statistical data that will be reported in the Clinical Study Report (CSR) for double blind treatment (Part 1) of Study WN28745 and will focus on the statistical methodology underlying the report. The efficacy and safety endpoints that will be the basis for comparing treatments will be defined in full in this document along with the populations of patients that are to be used in the analyses.

Dosing in study WN25203, investigating gantenerumab in prodromal Alzheimer's Disease (AD), was stopped in December 2014 due to a futility analysis. Consequently, recruitment into study WN28745 was stopped early. The final patient was randomized into study WN28745 on the 9th December 2015. Patients active in study WN28745 continued to receive study treatment until they discontinued from the study, finished the study, or transferred into the open label extension (OLE).

Although there will be reporting of study data in a variety of contexts beyond that of the CSR, such as the independent Data Monitoring Committee (iDMC), this document will not cover those contexts.

The description of layouts for the CSR outputs, the details about the underlying analysis datasets and programs, and the linking of production outputs to sections in the CSR are not within the scope of this document and will be covered in separate documents.

The language used in this statistical analysis plan (SAP) supersedes that in the protocol and protocol synopsis.

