4.4.1 Primary Efficacy Endpoint

The co-primary efficacy outcome measures are:

- The difference between Gantenerumab and Placebo treated patients in the mean change in ADAS-Cog 13 from baseline (Day 1) to Week 104 in the population of all randomized patients.

- The difference between Gantenerumab and Placebo treated patients in the mean change in ADCS-ADL from baseline (Day 1) to Week 104 in the population of all randomized patients.

For each of the co-primary endpoints, the absolute values, change from baseline and percentage change from baseline will be summarized by time-windowed visit.

In addition, the co-primary endpoints will also be analysed using a mixed model with repeated measures (MMRM). The model will use an unstructured variance – covariance matrix for the repeated measures allowing the inclusion of individuals with incomplete data. The following variables will be included in the modelling:

Dependant variable	ADAS-Cog 13 or ADCS-ADL
Independent variables	Treatment (placebo or Gantenerumab) APOE status (carrier or non-carrier) Baseline ADAS-Cog 13 or ADCS-ADL score Time (weeks relative to first dose in study) Treatment (placebo or Gantenerumab) by time (weeks relative to first dose in study) interaction

Patient, treatment and time will be treated as class variables. All data from all patients (as defined in Section 2.2) will be used, including data from Week 104/early termination visits.

A treatment-by-time interaction contrast will be used to estimate the difference between gantenerumab and placebo in the mean change from baseline at each visit. Least square means, standard errors, 95% confidence intervals will be reported for gantenerumab relative to placebo.

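### The Part 1 SAP repeats the efficacy analyses in APOE e4 carriers and non-carriers but plans no estimate of the difference between the two treatment effects

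*SAP*

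**What the plan says.** Part 1 SAP 4.5.8 is a single sentence. It covers safety as well, and for efficacy it says that "efficacy analysis will also be performed in the sub-group of patients who were enrolled in Japan and by APOE e4 carrier/non-carrier status". It names no comparison between the strata.

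The model to be repeated is the MMRM in SAP 4.4.1. APOE status enters it as a main effect only, and the sole interaction is treatment by time: "A treatment-by-time interaction contrast will be used to estimate the difference between gantenerumab and placebo in the mean change from baseline at each visit". The output is defined as follows: "Least square means, standard errors, 95% confidence intervals will be reported for gantenerumab relative to placebo". No p-value or alpha level is given. SAP 2.2 asks for results at Weeks 48, 72 and 104.

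The protocol goes further in two places.

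- Section 6.1.6: "An analysis will be performed to explore association of the treatment effect with patient genotypes to assess the influence of the APOE" e4 status, together with Fc-gamma receptor genotype, on the treatment effect. Results are to be summarized by genotype, and inferential statistics are optional.
- Section 6.1.7 lists APOE e4 status among the subgroups and permits an MMRM with "a treatment-by-subgroup interaction term, and a subgroup-by-time interaction terms included". It then limits when that model is used: "Such exploratory analyses will be performed primarily in the case where the descriptive statistics results indicate substantial differences between the subgroups".

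SAP section 1 sets the order of precedence: "The language used in this statistical analysis plan (SAP) supersedes that in the protocol and protocol synopsis".

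**The concern.** Whether APOE status influences the treatment effect is a question about the difference between two effects. Two separate gantenerumab-placebo intervals each address a different question, namely the size of the effect in that stratum. When the results are laid side by side, the natural comparison is whether one interval excludes zero and the other does not, and that comparison can disagree by chance when the two effects are equal.

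Readers will look at these panels closely. APOE status was a randomization stratification factor, the protocol reports that ARIA depends on it, and it sets the Part 2 titration scheme. At stake is a study report that suggests an APOE-dependent effect, or the absence of one, without showing how little the data can say about it.

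**Working it through.** **1. Is a contrast planned anywhere?** SAP 4.5.8 names none, and the SAP 4.4.1 model has no treatment-by-APOE term. Protocol 6.1.7 has a treatment-by-subgroup term, but the model is optional and depends mainly on the descriptive results. It also has no treatment-by-subgroup-by-time term, so it would give an interaction averaged over visits and not one at Week 48, 72 or 104. The Part 1 SAP does not mention it.

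**2. Inputs.** Protocol 6.1.1 and SAP 2.4 give an ADAS-Cog13 difference of 2.3 with SD 10.4, an ADCS-ADL difference of 2.5 with SD 10.9, 30% withdrawal and 500 patients per arm. Allocation was 1:1. The protocol synopsis and the introduction of the open-label extension SAP give 389 randomized. The carrier share p and the number evaluable at Week 104 are not in the documents. I assume p from 0.50 to 0.75 and show several evaluable numbers.

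**3. The plan's own power figure.** With 500 × 0.70 = 350 evaluable per arm, SE = 10.4 × √(2/350) = 0.786 and 2.3/0.786 = 2.93, so power = Φ(2.93 − 1.96) = 83.3%. The same steps for ADCS-ADL give 85.9%. Both meet the stated 80% or more. This only confirms that the SDs and effects are usable here.

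**4. Chance that exactly one stratum interval excludes zero, with equal true effects.** For m evaluable patients per arm:

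- SE(carriers) = SD × √(2/(mp)), and SE(non-carriers) = SD × √(2/(m(1−p)))
- P(interval excludes zero) = Φ(δ/SE − 1.96) + Φ(−δ/SE − 1.96)
- Exactly one = Pc(1 − Pn) + Pn(1 − Pc)

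With δ = 0, this is 2 × 0.05 × 0.95 = 9.5% at any size. With δ = 2.3 and SD 10.4:

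| Evaluable in total | p | SE carriers | SE non-carriers | Pc | Pn | Exactly one |
|---|---|---|---|---|---|---|
| 100 (m = 50) | 0.50 | 2.94 | 2.94 | 0.122 | 0.122 | 21.5% |
| 100 | 0.75 | 2.40 | 4.16 | 0.160 | 0.086 | 21.8% |
| 389 less 30% (m = 136.15) | 0.50 | 1.78 | 1.78 | 0.252 | 0.252 | 37.7% |
| 389 less 30% | 0.75 | 1.46 | 2.52 | 0.352 | 0.149 | 39.6% |
| 389 (m = 194.5) | 0.50 | 1.49 | 1.49 | 0.338 | 0.338 | 44.8% |
| 389 | 0.75 | 1.22 | 2.11 | 0.472 | 0.193 | 48.3% |

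A 95% interval for the contrast itself excludes zero 5% of the time whenever the two effects are equal, whatever their common size.

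**5. What the contrast would deliver.** SE(contrast) = √(SE carriers² + SE non-carriers²) = SE(overall)/√(p(1−p)), which is 2.0 to 2.3 times the SE of the overall treatment effect. For ADAS-Cog13:

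- All 389 evaluable: SE 2.11 to 2.44, 95% half-width 4.1 to 4.8 points, power 19% to 16% for a 2.3-point interaction.
- 389 less 30%: SE 2.52 to 2.91, half-width 4.9 to 5.7 points, power 15% to 12%.

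These are two-sample normal approximations. They ignore any gain from baseline adjustment or earlier visits.

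**The case against.** The strongest reply is that the contrast can already be recovered. Carriers and non-carriers are different patients, so if the MMRM is refitted in each stratum the difference in effects is the difference of the two estimates, with SE equal to the root of the summed squared SEs. SAP 4.4.1 plans to report the ingredients. This stands: the information is not lost, and the defect is that nobody is committed to presenting it.

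Second, Protocol 6.1.6 promises only exploration and by-genotype summaries, and the supersession clause cuts both ways: if it removes the interaction model in 6.1.7, it also removes the aim in 6.1.6. That is fair, but on either reading no contrast is guaranteed. If the protocol text survives, its model is optional and triggered by the very descriptive comparison that it should discipline. If it does not, the SAP has none.

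Third, the consequence is limited. Protocol 6.1.7 says that the primary and key secondary efficacy analyses will not be performed and that what remains is exploratory and descriptive. Protocol 1.4.1.2 regards a clinical effect at the Part 1 doses as very unlikely, which makes the 2.3-point scenario an upper case. All of this stands and keeps the point modest.

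Three stronger readings are tempting, and the documents do not support them.

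- A reader might infer that the SAP tests the wrong hypothesis. It specifies estimates and intervals, with no test.
- A reader might apply the planned sample size, where the same calculation gives 50-58%. That needs 700 evaluable patients, and only 389 were randomized.
- A reader might infer that losing patients by Week 104 makes disagreement more likely. With a 2.3-point effect it falls as numbers fall, from 45-48% at 389 to about 22% at 100.

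**Conclusion.** The concern holds as a gap in the planned output. The Part 1 SAP will estimate a treatment effect in each APOE stratum and plans no estimate of the difference between them, and it leaves out the protocol's optional interaction model.

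Comparing which interval excludes zero would mislead in about 9.5% of cases if there is no effect, and in about 22% to 48% if the effect is 2.3 points in both strata, against 5% for a direct contrast. These figures assume SD 10.4, a carrier share of 50-75%, 100 to 389 evaluable patients and a normal approximation. The carrier share matters little at these sizes. The true effect and the evaluable number matter most.

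The change is worth making because it is cheap and concerns a stratification factor. Part 1 efficacy is exploratory, so no formal conclusion of the trial depends on it.

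**What to change.** Add to Part 1 SAP 4.5.8:

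- For each co-primary endpoint, fit one pooled MMRM to all patients with treatment-by-APOE-by-time and its lower-order terms.
- Report the carrier minus non-carrier difference in treatment effect with its 95% interval at Weeks 48, 72 and 104, whatever the descriptive results show.
- Keep the stratum results as description, and base any statement on APOE modification on the contrast.
- Label the contrast exploratory and low-powered.

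The cost is one extra model per co-primary endpoint and no new data. The drawback is an imprecise result: a half-width of about 4 to 6 ADAS-Cog13 points and 12-19% power for a 2.3-point interaction, with 389 randomized and 0-30% loss. Greater loss would widen it further. Showing that width is useful, because separate panels do not display it.
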